#### 5.4.2 Primary Safety Analysis

All adverse events will be documented, reported, and categorized so that we may further understand the safety profile of this approach. The severity of each Adverse Event will be collected as well as its relationship to the SPR System. Any necessary treatment or intervention required and the resolution status of the adverse event will also be documented. Knowledge gained from this study will further refine consent forms and the risk benefit profile for future studies.

#### 5.4.3 Secondary Endpoint Analysis

As with the primary endpoint, we will analyze what effect, if any, the treatment has on pain interference (BPI9), Pain Free Passive Range of Motion, SF-36v2, BDI-II, the Patient Global Impression of Change scale, the SULCS, and subject satisfaction. QST testing is optional and thus an analysis will be completed if sufficient data are gathered.

Pain interference (BPI9), Pain Free Passive Range of Motion, SF-36v2, and BDI-II, the SULCS, and QST Testing are collected at the End of Trial Stage, 3-weeks, 12-weeks, 6-months, 9-months, and 12-months post IPG Stim ON. These secondary endpoints will be compared to the End of Sham. In addition, the pain interference (BPI9) is also collected at 6-weeks, 24-months and 36-months post IPG Stim ON and will be compared to End of Sham. As with the primary endpoints, subjects demonstrating a negative placebo effect for secondary endpoints will be compared to Baseline.

Results of the Patient Global Impression of Change scale and the subject satisfaction survey will be independently summarized to assess for a positive response indicating overall subject satisfaction with the system and therapy.

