#### **4.4.2 Secondary Endpoints**

Several secondary endpoints are being collected to gain a better understanding of what effect, if any, the SPR System may have on each measure. We intend to evaluate these instruments (described below) to determine their usefulness in our future larger pivotal study on the 2-stage implantable system.

Similar to the primary endpoint, all secondary endpoints will be assessed when stimulation is off (for at least one hour prior to the study visit). Stimulation therapy is administered for 6 hours per day and thus, it is off for the majority of the day. All endpoints will be measured when stimulation is off (for at least one hour prior to the study visit) such that the overall impact of daily stimulation on the subjects' primary and secondary endpoints can be assessed, rather than the potential immediate effect of having stimulation on.

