#### **4.4.2.1 Reduction in Pain Interference**

The degree to which shoulder pain interferes with daily activities will be assessed using Question 9 of the BPI (BPI9). This question asks the subject to rate the degree to which their pain has interfered with general activity, mood, walking ability, normal work, relations with other people, sleep, and enjoyment of life on a scale of 0 to 10, where 0 is “does not interfere” and 10 is “completely interferes”. The mean of these seven scores will be calculated to obtain the pain interference score. This pain interference endpoint will assist in assessing the impact of pain on activities of daily living and quality life. There is a strong relationship between the severity of post-stroke shoulder pain and BPI9 (Chae et al., 2007). Previous studies that evaluated the impact of neurostimulation therapy on post-stroke shoulder pain showed a significant reduction in the pain interference score when compared to controls (Chae et al., 2005; Yu et al., 2004). Similarly, we anticipate observing an improvement in pain interference in our study.

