#### **4.4.2.2 Pain-free passive range of motion (ROM)**

Pain will also be assessed using the pain-free shoulder external rotation ROM assessment. Following stroke, the shoulder often demonstrates a decreased range of motion (Fugl-Meyer, 1980). This decrease in ROM is associated with shoulder pain (Bohannon et al., 1986). In order to measure the pain-free passive ROM, stimulation will be turned off (for at least one hour prior to the study visit) [REDACTED]

Assessing the pain-free passive ROM is common in both clinical research and clinical practice as an objective measurement of pain (Chantraine et al., 1999; Faghri et al., 1994; Chae et al., 2005; Renzenbrink and IJzerman, 2004). Results will be analyzed to determine what impact, if any, the SPR System has on pain-free passive ROM. We expect no worsening of the pain-free ROM and will review the results to determine the usefulness of this measure for our pivotal study on the implantable system.

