**$P_1 < P_0$**

Alternatively, a negative placebo effect is present in any subject who has an increase in their BPI3 score from Baseline to the End of Sham:

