**$P_0$ =BPI pain score at Baseline**

**$P_1$ =BPI pain score at End of Sham**

#### **P2=BPI pain score at End of Trial Stim**

Then, subjects who demonstrate a positive placebo effect (or no placebo effect) will be considered SPR Trial Stage successes if they demonstrate a 2-point or greater decrease in their BPI3 score from the End of Sham to the End of Trial Stim:

$$P_1 - P_2 \geq 2$$

If the BPI3 score at End of Sham (P1) is less than 2 (e.g. the value is 1 or 0), then BPI3 at the End of Trial Stage (P2) must equal 0 to be considered a Trial Stage Success.

Alternatively, subjects who demonstrate a negative placebo effect (as evidenced by an increase in the BPI3 score during the sham period) will be compared to Baseline (Visit 1), rather than End of Sham. It is critical to compare to the Baseline BPI3 score for these subjects, to ensure that they have achieved pain reduction as a result of the stimulation therapy and not as a result of a placebo effect.

For these subjects, they will be considered SPR Trial Stage successes if they demonstrate a 2-point or greater decrease in their BPI3 score from Baseline to the End of Trial Stim:

$$P_0 - P_2 \geq 2$$

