#### **6.1.2.4 Overall study success**

Overall study success is defined by the success rate across all subjects participating in each stage, and is expected to exceed the historically observed success rate █ based upon previous and ongoing studies that demonstrated a █ success rate among subjects treated with stimulation therapy (Yu et al., 2001a; Chae et al, 2005; Chae et al., 2013; Wilson et al., 2014; as well as the present study and an unpublished randomized controlled trial).

A test of significance will be carried out to test the null hypothesis that the success rate █ or less versus the alternative that the true success rate exceeds █. In addition, a 95% confidence interval for the true success rate will be reported with the expectation that the lower limit of the interval will exceed █

All treatment failures, including any subjects who had an Implant Stage system removed due to an adverse event, will also be analyzed as part of this analysis.

Finally, a logistic regression will be reported, treating subject success as the binary outcome and baseline BPI as a possible explanatory variable. Other subject characteristics, such as time post-stroke, cortical vs. subcortical, right vs. left affected shoulder, and subluxation versus non-subluxation will be examined via a covariate analysis.

Secondary endpoints will be assessed using non-parametric tests. The Wilcoxon signed-rank test will be used to examine the difference of each endpoint for each subject. We will also investigate the mean improvement by reporting the results using a one-sample t-test.

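### If the switch to Baseline is applied endpoint by endpoint, the mean and rank tests of secondary endpoints lean towards worsening even when stimulation does nothing

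*Combined protocol and SAP*

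**What the plan says.** Section 5.4.3 sets End of Sham (Visit 4) as the comparator for BPI9, pain-free passive ROM, SF-36v2, BDI-II, SULCS and QST, then adds: "As with the primary endpoints, subjects demonstrating a negative placebo effect for secondary endpoints will be compared to Baseline". PGIC and satisfaction are summarised separately and are not involved.

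The flag itself is defined only in Section 5.4.1.1, on the primary pain score and with no threshold: "a negative placebo effect is present in any subject who has an increase in their BPI3 score from Baseline to the End of Sham". Section 5.4.1.2 gives the purpose of the switch, again for the binary BPI3 success definition: "to ensure that they have achieved pain reduction as a result of the stimulation therapy and not as a result of a placebo effect".

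Section 6.1.2.4 states the tests: "The Wilcoxon signed-rank test will be used to examine the difference of each endpoint for each subject", and "We will also investigate the mean improvement by reporting the results using a one-sample t-test". Section 6.1.2 carries the choice between Visit 4 and baseline into the interim analyses, and Section 6.2 makes the final analysis identical apart from the endpoints no longer collected. No adjusted null value, fixed-reference analysis, alpha or noise SD is given for secondary endpoints.

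On use, Section 4.4.2 says: "We intend to evaluate these instruments (described below) to determine their usefulness in our future larger pivotal study on the 2-stage implantable system". Section 4.4.2.1 says of BPI9: "Similarly, we anticipate observing an improvement in pain interference in our study". Section 4.4.2.2 says: "We expect no worsening of the pain-free ROM". Section 4.4.2.3 goes further for SF-36v2: the results are to be checked to make sure that quality of life does not deteriorate.

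**The concern.** Taking the stricter of two reference scores is cautious when the question is whether one subject is a responder. It is not neutral when the differences are averaged or ranked and tested against zero. A subject whose Visit 4 score was worse than Visit 1 by chance has that bad reading discarded. A subject whose Visit 4 score was better by chance keeps the good one. The reference is then too good on average, and a later unbiased score looks worse than it.

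Two uses are exposed. Where the plan looks for deterioration (SF-36v2 plainly, ROM to a lesser degree), the rule can produce it. Where the plan hopes for improvement, as with BPI9, the rule costs power and could lead the sponsor to discard an instrument that would have served the pivotal study.

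**Working it through.** **Inputs from the documents.** Up to 45 Trial Stage and approximately 18 Implant Stage subjects (Section 5.4); the reference rule (Section 5.4.3); the two tests (Section 6.1.2.4). The plan states no figure for this point that could be reproduced.

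**Assumed.** Normal scores with independent visit noise of SD 1, so all effects are in units of that SD; two-sided 0.05; t-test; Implant subjects unselected unless stated.

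**1. Direction.** Let P0, P1 and P2 be the scores at Baseline, End of Sham and the later visit, with lower better. On the endpoint-specific reading the reference is min(P0, P1), so

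P2 − reference = (P2 − P1) + max(P1 − P0, 0).

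The second term is never negative. If stimulation leaves the mean at its Visit 4 level, the expected change is above zero as soon as any subject worsens during sham. This sign needs no normality. Scales where higher is better mirror it.

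**2. Size with no sham effect.** The mean shift is 1/√π = 0.564. The SD of the difference is √(2 − 1/π) = 1.297. The noncentrality is 0.564 × √n / 1.297:
- n=45: 2.918 against a critical value of 2.015, giving significant worsening in 81%.
- n=18: 1.846 against 2.110, giving 41%.

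Simulation agrees. Signed-rank rates are about 79% and 38%. A fixed Visit 4 reference gives about 2.5%.

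**3. Dependence on the sham effect** (inert device; the sham change persists to the later visit):

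| Sham gain | Mean shift | False worsening, n=45 / n=18 |
|---|---|---|
| 0 | 0.56 | 81% / 41% |
| 0.5 SD | 0.35 | 42% / 18% |
| 1 SD | 0.20 | 17% / 8% |
| 2 SD | 0.05 | 4% / 3% |

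**4. BPI3-flag reading.** The shift becomes ρ × 0.564, where ρ is the correlation of the endpoint's noise with BPI3 noise: 0, 0.17 and 0.28 at ρ = 0, 0.3 and 0.5. False worsening at n=45 is 2.5%, 12% and 27%. At ρ = 0 there is no bias.

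**5. Power.** For a true benefit of 0.75 SD and no sham effect, the switched reference gives about 15% / 8% (n=45 / n=18) against 94% / 56% with fixed Visit 4. For 1.5 SD the loss is small at n=45 (over 99% against 100%) and larger at n=18 (82% against 99%). A true benefit of 0.25 SD is shown as significant worsening in about 35% / 16%; at 0.5 SD this is 5% / 4%.

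**6. Implant Stage selection.** Only Trial Stage successes with returning pain advance, which pulls the other way. In an assumed no-effect model (true BPI3 mean 6.5, between-subject SD 1.5, visit noise 1 or 1.5 points, two follow-up scores meeting the return-of-pain rule), the shift towards worsening is 0.56 at ρ = 0, about 0.40 to 0.42 at 0.3 and 0.21 to 0.25 at 0.6. A fixed Visit 4 reference then shows a false improvement of 0.14 to 0.15 at ρ = 0.3 and 0.26 to 0.30 at 0.6.

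No rate is given for SULCS and QST, which cover only subjects enrolled after those tests were added.

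**The case against.** **The rule has a reason and errs against the device.** Both are true. The reason is given for the binary BPI3 definition, where it can stay, and the caution applies only to claims of benefit. It does not help when a result is read for worsening.

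**The flag may mean BPI3.** It is the only definition in the plan, and on that reading the bias may be nil. A reader might infer that the secondary tests are biased whatever the flag means; the documents do not support that. The wording in Section 5.4.3 favours an endpoint-specific flag but does not settle it.

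**The large percentages rest on assumptions.** This stands. The documents give no SD, correlation or alpha, and 81% requires no sham effect at all. It should not be read as a forecast for this trial.

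**These endpoints decide nothing.** Mostly right. A reader might infer that study success is compromised, but Trial Stage, Implant Stage and overall success are binary BPI3 outcomes that these tests do not touch. Section 4.4.2.2 also says that ROM is reviewed for its usefulness as a measure, so SF-36v2 is the one endpoint with an explicit aim of ensuring no deterioration.

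**Visit 4 alone is not a clean comparator.** Correct, and it limits the remedy. With an inert device, a 0.5 SD sham worsening that resolves by the later visit gives false benefit against Visit 4 in 64% / 29% (n=45 / n=18). A 0.5 SD sham gain that fades gives false worsening at the same rates.

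**Conclusion.** The concern holds on condition. If the flag is applied endpoint by endpoint, the t-test and signed-rank test of secondary endpoints are not centred on zero under no effect, and they lean towards worsening. The direction follows from the rule itself, given that stimulation leaves the mean at its Visit 4 level. The size depends on the assumed noise and on what sham does, and in the unselected case runs from about 81% / 41% false worsening with no sham effect down to 4% / 3% with a persistent 2 SD gain. If the BPI3 flag governs, the effect ranges from none upwards with the noise correlation. Selection into the Implant Stage reduces the shift there.

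The consequence is moderate: weaker piloting of instruments and possible false signals of deterioration, with no effect on any success criterion. The change is worth making because it is cheap and nothing else in the plan corrects the rule. Confidence in the size is medium.

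**What to change.** For mean and rank tests of secondary endpoints:

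- Use End of Sham (Visit 4) as the reference for every subject, and report the same test and 95% confidence interval against Baseline (Visit 1) for every subject alongside. Do not switch subject by subject. The undefined secondary-endpoint flag is then not needed for these tests.
- Keep the lower-of-two rule for the binary responder endpoint only.
- Claim benefit only if both comparisons are significant in the same direction. With the transient 0.5 SD sham worsening above, this cuts false benefit from 64% / 29% to about 2.4% / 1.8%.
- If the two comparisons disagree in either direction, report a possible sham-period change and do not attribute it to stimulation from one comparison alone.
- Do not conclude that there is no worsening from a non-significant result. With a true worsening of 0.5 SD, neither interval would lie wholly on the worse side in 20% / 56% of trials. Report the worse limit of each interval. With a zero estimate it is t × √(2/n): 2.015 × 0.211 = 0.42 SD at n=45 and 2.110 × 0.333 = 0.70 SD at n=18.
- State alpha and sidedness.

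Cost: wording and one extra table, with no new data. Power for a 0.75 SD benefit with no sham effect is 89% / 39% with both comparisons required, instead of 94% / 56% with Visit 4 alone, and against 15% / 8% under the switched reference. If sham itself worsens scores by a persistent 0.5 SD, requiring both leaves only 21% / 9%. Fixed references do not remove Implant Stage selection, which should be named as a limitation of those results.

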### 6.0 STATISTICAL METHODS

#### 6.1 Planned Interim Analysis

##### 6.1.1 Interim Safety Review (annual)

The Chairman of the DSMB (described further in Section 11) will review and adjudicate the accumulating safety data at least annually (once enough safety data have accumulated) to monitor for trends that would warrant modification or termination of the trial and will convene the DSMB if any concerns regarding the safety of the trial arise, such as a UADE.

We will continue enrollment if the safety profile is as expected. We may elect to close enrollment based upon the recommendations of our DSMB safety

evaluation or if we find that changes to the SPR System are necessary prior to enrolling additional subjects.

#### **6.1.2 Interim Safety and Efficacy Analysis (all subjects)**

Once all subjects who have advanced from the Trial Stage to the Implant Stage have completed the 12-week IPG Stim On evaluation (Visit 10), an interim analysis will be conducted by our DSMB to monitor safety and clinical efficacy. End of Trial Stage data (Visit 5) will be compared to data collected at the End of Sham (Visit 4) or baseline, where necessary. In addition, efficacy data collected at Visit 12 will be compared to data collected at the End of Sham (Visit 4) or baseline, where necessary.

In addition, similar analyses will be conducted once all subjects have completed the 6, 12, and 24 months IPG Stim On evaluations.

The following analyses will be conducted on the interim data for all subjects.

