
	
Implant Stage, subjects will receive the fully implantable SPR Implant Stage system and be followed for 3 years.
 
All primary and secondary endpoints will be assessed at baseline and again at the completion of the sham period and the active stimulation period of the SPR Trial Stage. In addition, primary endpoints will be evaluated via monthly phone calls during the Trial Stage follow-up period as well as at visits during the SPR Implant Stage (3-weeks, 6-weeks, 12-weeks, 6-months, 9-months, and 12-months post IPG Stim ON). In addition, long-term follow-up will be conducted on an annual basis at 24-months and 36-months post IPG Stim ON.
 
Primary efficacy of the Trial Stage will be determined at the end of the Trial Stage. Primary efficacy of the Implant Stage will be determined at 12-weeks post IPG Stim ON. All Implant Stage subjects will continue to be evaluated at 6, 9, and 12-months post IPG Stim ON follow-up visits and annually for 36 months to determine the long-term efficacy and safety profile of the SPR Implant System and to evaluate the effect of dosage (number of hours of use each day) on treatment effect. Adverse events will be assessed at all follow-up visits.

Number of Sites	Up to 5 Investigational Sites will be enrolled
Number of Subjects	45 subjects will participate in the SPR Trial Stage. Although we expect to yield approximately 18 subjects with an implantable system (SPR Implant Stage), all eligible Implant Stage subjects will be permitted to advance to the Implant Stage.

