#### 4.4 Study Endpoints

##### 4.4.1 Primary Endpoints

###### 4.4.1.1 Reduction in pain intensity (Brief Pain Inventory)

The primary endpoint of the study is reduction in pain intensity over the past week as measured using the 11-point numerical rating scale of the Brief Pain Inventory (BPI3). The BPI is a widely used and validated assessment designed to measure pain intensity and the interference of pain on daily activities and moods (Cleeland and Ryan, 1994).

The BPI is recommended by the Initiative on Methods, Measurement, and Pain Assessment in Clinical Trials (IMMPACT) panel and has demonstrated validity and reliability across many cultures and languages (Cleeland and Ryan, 1994; Tan et al., 2004; Dworkin et al., 2005). The IMMPACT panel was assembled to develop consensus recommendations to improve and standardize the design and conduct of clinical trials involving treatments for pain. Invited participants included academic centers, regulatory agencies, the National Institutes of Health, the US Veterans Administration, and industry representatives. In addition, the BPI has been used in many chronic pain studies, including those for post-stroke shoulder pain, which demonstrated a significant reduction in pain intensity as compared to a standard of care control (Chae et al., 2005; Yu et al., 2004).

All subjects will be evaluated for a reduction in their worst pain intensity in the previous week (BPI3) at several key study visits: (1) at the completion of the 3-week sham period (Visit 4) to evaluate the placebo effect; (2) at the completion of the 3-week SPR Trial Stage stimulation period (Visit 5) to determine if the subject has met the criteria to be a Trial Stage Success; (3) during the Trial Stage follow-up period to assess for Implant Stage eligibility, and (4) at 3-weeks (Visit 8), 6-weeks (Visit 9), 12-weeks (Visit 10), 6-months (Visit 11), 9-months (Visit 12), 12-months (Visit 13), 24-months (Visit 14), and 36 months (Visit 15) following

the initiation of IPG Stimulation to determine efficacy of the implantable system. The BPI will be administered with stimulation turned off (for at least one hour prior to the study visit) and subjects will be instructed to focus on their shoulder pain when responding to the questions presented in the BPI.

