#### **4.5.3.8 12-Week IPG Stim On (Visit 10)**

Following 12 weeks of IPG stimulation, subjects will return for evaluation of primary and secondary endpoints including the BPI, Pain Free Passive Range of Motion, SF-36v2, the BDI-II, the Patient Global Impression of Change scale, and a Subject Satisfaction Survey. Subjects will also be queried for medication usage and adverse events. To assess participant compliance with the stimulation regimen, [REDACTED] will be recorded in the subject records. The 12-week visit will serve as the primary efficacy analysis for the SPR System.

At the end of the visit, the number of daily hours of stimulation will be modified according to the pain relief reported by the subject:

- If the subject's BPI Question #3 score is  $\leq 2$ , the dosage (number of hours of stimulation per day) will be reduced from 6 hours to 4 hours.
- If the subject's BPI Question #3 score is greater than 2 but at least two points less than the baseline score (i.e., still reporting clinically significant pain relief), the dosage will remain at 6 hours per day.

- If the subject's BPI Question #3 score is not 2 points less than it was at baseline, the dosage will remain at 6 hours and the system will be checked for any technical problems.

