#### **4.5.3.10 9-Month IPG Stim ON (Visit 12)**

Following 9 months of IPG stimulation, subjects will return for evaluation of primary and secondary endpoints including the BPI, Pain Free Passive Range of Motion, SF-36v2, BDI-II, and the Patient Global Impression of Change scale. Subjects will also be queried for medication usage and adverse events. To assess participant compliance with the stimulation regimen, [REDACTED] will be recorded in the subject records.

At the end of the visit, the number of daily hours of stimulation will be modified according to the pain relief reported by the subject:

- [REDACTED] If the subject's BPI Question #3 score is  $\leq 2$ , the dosage [REDACTED]
- [REDACTED] If the subject's BPI Question #3 score is greater than 2 but at least two points less than the baseline score (i.e., still reporting clinically significant pain relief), the dosage [REDACTED]
- [REDACTED] If the subject's BPI Question #3 score is not 2 points less than it was at baseline, the dosage [REDACTED]

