##### **6.1.2.3 SPR Implant Stage Success**

Implant Stage success for each subject is the binary outcome pertaining to success (a 2-point or greater decrease in BPI3) or failure (a decrease of less than two points, no change in BPI3, or increase of BPI3) during the Implant Stage of the study. This endpoint will be compared between 12-weeks IPG Stim ON (Visit

10) and the End of Sham (Visit 4) for subjects who demonstrate either no placebo or a positive placebo effect. For subjects in whom a negative placebo effect was observed, results will be compared against Baseline (Visit 1).

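### Section 6.1.2 starts the interim analysis at 12 weeks (Visit 10) but takes the implant efficacy data from Visit 12, which is the 9-month visit

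*Combined protocol and SAP*

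**What the plan says.** Section 6.1.2 gives the trigger: once all subjects who advanced to the Implant Stage "have completed the 12-week IPG Stim On evaluation (Visit 10), an interim analysis will be conducted" by the DSMB. For the implant data, the same paragraph says that "efficacy data collected at Visit 12 will be compared to data collected at the End of Sham (Visit 4) or baseline, where necessary". It then adds that "similar analyses will be conducted once all subjects have completed the 6, 12, and 24 months IPG Stim On evaluations".

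Section 4.4.1.1 sets out the visit numbering: "12-weeks (Visit 10), 6-months (Visit 11), 9-months (Visit 12), 12-months (Visit 13"). The heading and text of Section 4.5.3.10 agree that Visit 12 is the 9-month visit.

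The Synopsis says: "Primary efficacy of the Implant Stage will be determined at 12-weeks post IPG Stim ON". Section 4.5.3.8 (Visit 10) says: "The 12-week visit will serve as the primary efficacy analysis for the SPR System". Section 6.1.2.3 opens its comparison with "This endpoint will be compared between 12-weeks IPG Stim ON" and identifies that as Visit 10. Section 5.4.1.4 defines Implant Stage success at the same visit. Section 6.2 describes the final analysis as a repeat of the one on the 12-week data.

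Section 6.1.2.4 adds Wilcoxon signed-rank and one-sample t-tests on the secondary endpoints and names no visit for them.

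On the companion item, Section 5.4.3 lists SULCS and QST at the end of the Trial Stage and then at 3 weeks, 12 weeks, 6, 9 and 12 months after IPG Stim ON. Sections 4.4.2.8 and 4.4.2.9 schedule both at Visits 1, 4, 5, pre-6, 9, 11 and 13.

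**The concern.** Section 6.1.2 is the written instruction for the DSMB's efficacy look, and within one paragraph it names two different implant visits. For Implant Stage success, Section 6.1.2.3 removes the doubt. For the other implant-stage comparisons in that look, the sentence naming Visit 12 is the only text within Section 6.1.2 that gives a visit. Pain interference, pain-free passive range of motion, SF-36v2, BDI-II and PGIC are collected at both Visit 10 and Visit 12, so an analyst could run the wrong visit and see nothing amiss in the output.

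The two visits are not interchangeable. Subjects are instructed to use the system for 6 hours a day from Visit 7. At the end of Visits 10 and 11, daily hours are reviewed against the BPI3 score. A Visit 12 value may therefore have been recorded under a different regimen from a Visit 10 value.

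In Section 5.4.3, an analyst looking for SULCS and QST is sent to visits with no scheduled data and is not told of one visit that has them.

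**Working it through.** There is no planned figure to reproduce. The check is a cross-reference of visits plus nominal timing.

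**Visit named for the 12-week look**

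| Place | Visit or time |
|---|---|
| 6.1.2, trigger | Visit 10, 12 weeks |
| 6.1.2, implant efficacy data | Visit 12 (9 months by 4.4.1.1 and 4.5.3.10) |
| 4.5.3.8, primary efficacy analysis | Visit 10, 12 weeks |
| 5.4.1.4, success definition | Visit 10, 12 weeks |
| 6.1.2.3, success comparison | Visit 10, 12 weeks |
| 6.2, reference back | 12 weeks |
| 6.1.2, later looks | 6, 12 and 24 months |
| 6.1.2.4, secondary-endpoint tests | none named |

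Only one entry points to 9 months, and no planned look falls there.

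**Timing.** Assumption: nominal weeks after IPG Stim ON, since the visit windows in Table 7 are redacted. Visit 10 = 12, Visit 11 (6 months) = 26, Visit 12 (9 months) = 39.

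- Visit 10 to Visit 12: 39 − 12 = 27 weeks.
- Visit 10 trigger to the 6-month look, for the same last subject: 26 − 12 = 14 weeks.
- If the first look waits for Visit 12, it follows the due date of the 6-month look by 27 − 14 = 13 weeks.

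So there are two literal outcomes. If data are cut at the trigger, at least the last implanted subject has no Visit 12 value. If the look waits for Visit 12, it comes after the 6-month look that it should precede.

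**SULCS and QST after implant**

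- Listed in 5.4.3: Visits 8, 10, 11, 12, 13 (5 visits).
- Scheduled in 4.4.2.8 and 4.4.2.9: Visits 9, 11, 13 (3 visits).
- Listed but not scheduled: Visits 8, 10, 12, so 3 of 5.
- Scheduled but not listed: Visit 9, so 1 of 3. Section 5.4.3 adds 6 weeks for BPI9 only.

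The visit sections agree: SULCS and QST appear under Visits 9, 11 and 13 and not under Visits 8, 10 and 12. Those last three describe their endpoints in non-exhaustive terms, but the explicit visit lists in 4.4.2.8 and 4.4.2.9 settle it. The SULCS and QST rows of Table 6 were not used, because the columns are broken in the available text.

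**The case against.** The strongest reply is that Visit 12 is an evident slip for the 12-week visit and corrects itself. The Synopsis and Sections 4.5.3.8, 5.4.1.4, 6.1.2.3 and 6.2 all say 12 weeks, and a careful analyst would follow them. This stands for Implant Stage success. It stands less well for the secondary-endpoint tests, because 6.1.2.4 names no visit and 6.1.2.3 covers only the binary rule.

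The practical size may also be small. Section 4.7 expects about 18 implanted subjects and about 7 years of enrollment. If implants were spread evenly over 7 × 52 = 364 weeks (an assumption), 18 × 27/364 = 1.3, so one or two subjects would lack Visit 12 at the trigger. Clustering of implants late in the study would raise this. The documents give no implant dates, so only the minimum of one is firm.

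The point about stimulation hours is limited too. The rule at Visit 10 is visible, but the resulting action at Visit 11 is redacted, so only possible changes can be claimed.

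On SULCS and QST, collection is set consistently elsewhere, QST is optional, and Section 4.4.2 presents the secondary endpoints as exploratory. A reader might infer that the Visit 9 data are lost or have no planned comparison. The documents do not support that: Section 5.4 promises analysis of all secondary endpoint data, 5.4.3 gives the comparator (End of Sham, or Baseline after a negative placebo effect), and 6.1.2.4 gives the test. Only the time point is mislisted.

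**Conclusion.** The sentence in 6.1.2 is wrong as written and should be corrected. It names a visit nominally 27 weeks after the trigger, contradicts the sections that define this analysis, and matches none of the later looks. Its effect is confined to the implant-stage comparisons other than Implant Stage success.

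Two stronger readings are tempting. One is that the primary endpoint has moved to 9 months or is undefined; 5.4.1.4 and 6.1.2.3 rule that out. The other is that a stopping decision would rest on the wrong data; the plan states no efficacy stopping boundary, so this cannot be shown.

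The 27- and 13-week figures assume nominal visit timing. The SULCS and QST mismatch is real but minor, and because QST is optional it falls mainly on SULCS.

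**What to change.** In Section 6.1.2, change Visit 12 to Visit 10 in the sentence on implant efficacy data. The paragraph then agrees with its trigger and with 5.4.1.4, 6.1.2.3 and 6.2.

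In Section 5.4.3, give SULCS and QST their own sentence. List their analysed post-sham visits as Visit 5 and post-implant Visits 9, 11 and 13, with the comparator already stated there. If Visit pre-6 is mentioned, identify it only as a pre-implant assessment outside the End of Sham comparison, since the plan states no such comparison for it.

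The cost is wording in two places, with no change to visits, data collection or sample size. Making the change before the interim data are examined also avoids any appearance that the visit was chosen afterwards.
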